8.10.2 Emergency Room Visits and Revascularization Procedures

Listings will be provided for all reported emergency room visits and revascularization procedures.

8.10.3 Death

A listing of all deaths will be provided. The listing will include date of death, primary cause of death and any associated AE.

8.10.4 Clinical Laboratory Tests

Clinical laboratory tests to be performed in this study are listed in detail in Appendix C.

For central laboratory test summaries by visit, the central laboratory measurements at scheduled visits will be used if available. The visit information from the central laboratory will be used to determine whether a visit is scheduled or unscheduled.

If a laboratory result from a visit is retested and the central laboratory subsequently determines the original result to be valid, the original result for that visit will be used in analysis, and the second (i.e. ‘retested’) value will be ignored. Otherwise, if the central laboratory detects an error through the retesting, the retested value will be used in analysis as the measurement for that visit.

The baseline central laboratory value is defined as the last non-missing central laboratory value collected on or before the date of the first dose of study medication.

8.10.4.1 Serum Chemistry

Serum chemistry tests will be performed at S1, S3, Randomization/Baseline and all scheduled visits during the study, including the FU Visit. Tests may also be done at unscheduled visits.

All serum chemistry results will be summarized by treatment group with descriptive statistics at each scheduled visit, and for the change from baseline to the corresponding time points.

The incidence of laboratory test results in ranges of interest will be summarized by treatment group. These summaries will include but are not limited to the following:

- Serum potassium < 3.0, < 3.5, < 3.8, > 5.0, and ≥ 5.5 mEq/L
- Serum magnesium < 1.4, < 1.2, and < 1.0 mg/dL
- Serum calcium > 10.2 mg/dL

Laboratory shift tables from Baseline to End of Treatment will be provided for selected laboratory results.

Listings will be provided for all serum chemistry parameters. Listings will include test results at both scheduled and unscheduled visits.

8.10.4.2 Hematology

Hematology tests will be performed at S1, Randomization/Baseline, Week 4 and Week 12/ET. Tests may also be done at unscheduled visits.

All hematology results will be summarized by treatment group with descriptive statistics at Randomization/Baseline, Week 4, and at Week 12/ET, and for the change from Baseline at each time point.

A listing of hematology will be provided. The listing will include test results at both scheduled and unscheduled visits.

8.10.4.3 Special Laboratory Tests

The following special laboratory tests will be conducted for this study: NT-proBNP; aldosterone and plasma renin activity; spironolactone level.

Special laboratory test results will be summarized by treatment group with descriptive statistics at each time point at which they were collected, and for change from Baseline to each post-baseline time point.

A listing for special laboratory tests will be provided.

8.10.4.4 24-hour Urine

24-hour urine for sodium, potassium, creatinine, and albumin tests will be performed at Randomization/Baseline.

Raw test results will be adjusted to correct for the actual observed duration of the collection time in hours. The 24-hour-adjusted values for sodium, potassium, creatinine, and albumin will be calculated as:

$$24\text{-hour-adjusted value} = [(\text{raw test value}) / (\text{sample collection time in hours})] \times 24$$

The 24-hour ACR will be calculated as:

$$\text{24-hour ACR} = (\text{24-hour albumin} / (\text{24-hour creatinine}))$$

Descriptive summary statistics will be presented at Baseline, by treatment group, for the following variables:

- 24-hour-adjusted sodium, potassium, creatinine, and albumin
- Ratio of 24-hour urine albumin and creatinine

A listing for 24-hour urine results will be provided.

8.10.4.5 Spot Urine (ACR)

Spot urine will be collected for measuring ACR at Randomization/Baseline, Week 4, Week 8, and Week 12/ET. At Randomization/Baseline spot urine samples will be from 2 first morning voids, collected 1 and 2 days prior to the Randomization/Baseline Visit. At Weeks 4, 8, and 12, spot urine samples will be from 3 first morning voids collected on the day of the visit and on 1 and 2 days prior to the visit.

Mean values will be calculated for albumin and creatinine over the spot urine samples collected for each visit. The value of ACR at a visit will be the mean albumin value divided by the mean creatinine value.

Spot urine ACR will be summarized by treatment group with descriptive statistics at Randomization/Baseline, Week 4, Week 8, and Week 12. Note that change in ACR from Randomization/Baseline to Week 12/ET is an efficacy endpoint in this study (see Section 6.1.3).

A listing for spot urine results will be provided.

8.10.5 ***Vital Signs***

Blood pressure summaries have been described in Section 8.9.

Heart rate will be summarized, by treatment group, with descriptive statistics for each scheduled visit, and for the change from baseline to the corresponding time points.

Height is assessed only at S1 and will be summarized as part of the baseline characteristics.

Weight is assessed at S1, Randomization/Baseline, and at Week 12/ET. Weight will be summarized, by treatment group, with descriptive statistics for Randomization/Baseline and Week 12/ET, and for the change from baseline to Week 12/ET.

A listing for vital signs, weight and height will be provided.

8.10.6 Physical Examination

Physical examinations will be performed at S1 and Week 12/ET.

Abnormalities found in physical examinations will be summarized by treatment group at Screening and at Week 12/ET. Clinically significant abnormalities after the start of study drug are reported as AEs and summarized as described in Section 8.10.

A listing for physical examination will be provided.

8.10.7 12-lead Electrocardiogram (ECG)

Standard 12-lead ECGs will be performed in all subjects at the S1 and Week 12/ET. Number and percentage of subjects with normal/abnormal and clinically significant abnormal ECG findings will be summarized at S1 and Week 12/ET.

A listing for 12-lead ECG will be provided.

8.10.8 Pregnancy Test

A listing for all pregnancy tests will be provided.

APPENDIX A: SCHEDULE OF EVENTS

| Study Period | Screening/Run-in Period | | | Screening/ Randomization | Double-Blind Treatment | | | | | | | | Follow-Up ^a | Unscheduled Visit |
|---|---------------------------------|----|-----|-----------------------------|------------------------|------------------------|----------------|----------------|----------------|----------------|----------------|------|------------------------|-------------------|
| | Visit/Day/Week | S1 | S2 | | S3 | S4/BL(D0) ^b | W1 | W2 | W3 | W4 | W6 | W8 | | |
| Window | 1 week (≥ 4 d but ≤ 10 d) apart | | | | ±3 d | ±3 d | ±3 d | ±3 d | ±7 d | ±7 d | ±7 d | ±7 d | +7 d | |
| Study Activity | | | | | | | | | | | | | | |
| Informed Consent | X | | | | | | | | | | | | | |
| IWRS Entry | X | X | X | X ^c | X | X | X | X | X | X | X | X | X | X |
| Inclusion Exclusion Criteria | X | | | X ^d | | | | | | | | | | |
| Demographics | X | | | | | | | | | | | | | |
| Medical History | X | | | | | | | | | | | | | |
| Heart Rate (resting for 5 minutes) | X | X | X | X | X | X | X | X | X | X | X | X | X | X |
| Height | X | | | | | | | | | | | | | |
| Weight | X | | | X ^d | | | | | | | | X | | X, optional |
| Physical Examination | X | | | | | | | | | | | X | | X, optional |
| 12-lead Electrocardiogram | X | | | | | | | | | | | X | | X, optional |
| AOBP performed onsite (triplicate measurements) ^e | X | X | X | X | X ^f | X ^f | X ^f | X ^f | X ^f | X ^f | X ^f | X | X | X |
| SMBP performed onsite and HBP training, as necessary (triplicate measurements) ^g | X | X | X | X | X | X | X | X | X | X | X | X | | X, if available |
| SMBP performed at home (triplicate measurements) ^h | | X | X | X | X | X | X | X | X | X | X | X | | X, if available |
| Potassium ⁱ | L&C | | L&C | L&C ^d | L&C | L&C | L&C | L&C | L&C | L&C | L&C | L&C | L&C | L&C |
| Serum Chemistry (including creatinine, eGFR) | C | | C | C ^d | C | C | C | C | C | C | C | C | C | C, optional |
| Hematology | C | | | C ^d | | | | C | | | | C | | C, optional |
| Serum Pregnancy | C | | | | | | | | | | | C | | |
| NT-proBNP | | | | C ^d | | | | | | | | C | | |

Schedule of Events (Cont'd)

| Study Period | Screening/Run-in Period | | | Screening/ Randomization | Double-Blind Treatment | | | | | | | | Follow-Up ^a | Unscheduled Visit |
|--|---------------------------------|----|----|-----------------------------|------------------------|------------------------|------|------|------|------|------|------|------------------------|-------------------|
| | Visit/Day/Week | S1 | S2 | | S3 | S4/BL(D0) ^b | W1 | W2 | W3 | W4 | W6 | W8 | | |
| Window | 1 week (≥ 4 d but ≤ 10 d) apart | | | | ±3 d | ±3 d | ±3 d | ±3 d | ±7 d | ±7 d | ±7 d | ±7 d | +7 d | |
| Study Activity | | | | | | | | | | | | | | |
| Aldosterone and plasma renin activity | | | | C ^d | | | | | | | | | | |
| Spironolactone Level | | | | | C | | | C | | C | | C | | |
| Urinalysis | C | | | C ^d | | | | | | | | C | | |
| 24 hr urine collection container (dispense and train) | | | X | | | | | | | | | | | |
| 24 hr urine for sodium, potassium, creatinine, albumin (for ACR) | | | | C ^d | | | | | | | | | | |
| ACR urine sample collection cups (dispense and train) | | | X | | | | X | | X | | X | | | |
| Urine ACR (3 first morning void samples) | | | | C ^{d,k} | | | | C | | C | | C | | |
| Urine pregnancy test | | | | X ^d | | | | | | | | | | |
| EQ-5D-5L Questionnaire ^l | | | | X ^d | | | | | | | | X | | |
| IWRS Randomization to Patiromer / Placebo | | | | X ^d | | | | | | | | | | |
| Patiromer/placebo Dispensing ^m | | | | X ^d | X | X | X | X | X | X | X | | | X, optional |
| Spironolactone Dispensing ⁿ | | | | X ^d | X | X | X | X | X | X | X | | | X, optional |
| Drug Accountability | | | | | X | X | X | X | X | X | X | X | | X, optional |
| Dietary Counselling | X | X | X | X ^d | X | X | X | X | X | X | X | X | | X |

Schedule of Events (Cont'd)

| Study Period | Screening/Run-in Period | | | Screening/Randomization | Double-Blind Treatment | | | | | | | | Follow-Up ^a | Unscheduled Visit | |
|--------------------------------|--|----|----|-------------------------|------------------------|------------------------|-----------|-----------|-----------|-----------|-----------|-----------|------------------------|-------------------|-----|
| | Visit/Day/Week | S1 | S2 | | S3 | S4/BL(D0) ^b | W1 | W2 | W3 | W4 | W6 | W8 | | | W10 |
| Window | 1 week (≥ 4 d but ≤ 10 d) apart | | | | ± 3 d | ± 3 d | ± 3 d | ± 3 d | ± 3 d | ± 7 d | ± 7 d | ± 7 d | ± 7 d | +7 d | |
| Study Activity | | | | | | | | | | | | | | | |
| AE Assessment | X | X | X | X | X | X | X | X | X | X | X | X | X | X | X |
| Record Concomitant Medications | X | X | X | X | X | X | X | X | X | X | X | X | X | X | X |

AOBP = automated office blood pressure; ACR = albumin to creatinine ratio; AE = adverse event; BP = blood pressure; C = central laboratory; D (or d) = day; D0 = Day 0; ET = Early Termination Visit; hr = hour; IWRS = Interactive Web Response System; L = local; R = Randomization; S = Screening Visit; SMBP = subject-measured blood pressure.

- ^a If a subject completes the Follow-up Visit prior to 2 Weeks, the subject will receive a Follow-up Phone Call at 2 weeks after Week 12 or ET Visit (+ up to 7 days)
- ^b If hemolysis of the local sample is detected or is suspected), subject is not randomized at S4, and a repeat of the potassium measurement from a separate blood draw will be performed within 1 day. If subject qualifies they will be randomized and this Visit will be the Randomization/Baseline (Day0) Visit. All assessments at S4, aside from the repeat potassium level, will be considered the baseline.
- ^c For subjects who meet all inclusion criteria, this Visit becomes the Randomization/Baseline Visit (Day0). For subjects who screen fail at this visit, this is Visit S4.
- ^d Assessment or event will occur only if subject meets all inclusion criteria.
- ^e Measured automatically using office device (while unobserved by the study staff) after 5 minutes of quiet seating prior to triplicate measures.
- ^f Review AOBP results and adjust study medications according to titration rules.
- ^g HBP device issued on Visit S1 and measured by subject using their issued HBP device (while unobserved by the study staff) after 5 minutes of quiet seating prior to triplicate measures. HBP monitors are collected from subjects at the Visit Week-12.
- ^h HBP will be measured by subject twice daily (e.g., at approximately 08:00 hrs and 20:00 hrs) after sitting quietly for at least 5 minutes. The subject will perform triplicate measures, 1 minute apart. HBP training will be performed at the first screening visit and retraining can be performed at any Visit, as needed. HBP monitors are collected from subjects at the Visit Week-12.
- ⁱ If hemolysis of the local sample is detected or is suspected, the sample must be repeated within 1 day for reassessment of potassium.
- ^j Review potassium results and adjust study medications according to titration rules..
- ^k One of the ACR measurements will be from the 24-hour urine collection.
- ^l Subjects will complete the EQ-5D-5L questionnaire before study staff performs any clinic or study assessments to avoid biasing the subjects' responses.
- ^m On Day1 patiomer/placebo two packets QD will be taken at home with food and at least 3 hours before or 3 hours after other oral medications including spironolactone.
- ⁿ On Day 1 spironolactone (25 mg QD) will be taken at home and increased to 50 mg at Week 3 for subjects with blood pressure ≥ 120 mmHg..

APPENDIX B: IMPUTATION OF DATES

1 Imputation of Missing/Partially Missing Adverse Event Dates

1.1 Incomplete Start Date:

Partially missing AE start/stop dates will be imputed in the ADaM dataset for AEs, according to the rules below. However, listings of AE data will present the date as is, with missing date components left blank.

If the AE end date is complete with no missing year, month, or day, and a partially missing start date imputed by the rules below is after the AE end date, then the imputed start date will be equal to the end date.

Missing day and month

- If the year is the **same** as the year of the first dosing date, then the day and month of the first dosing date will be assigned to the missing fields.
- If the year is **prior to** the year of first dosing date, then December 31 will be assigned to the missing fields.
- If the year is **after** the year of first dosing, then January 1 will be assigned to the missing fields.

Missing day only

- If the month and year are the **same** as the year and month of first dosing date, then the first dosing date will be assigned to the missing day.
- If either the year of the partial date is **before** the year of the first dosing date or the years of the partial date and the first dosing date are the same but the month of partial date is **before** the month of the first dosing date, then the last day of the month will be assigned to the missing day.
- If either the year of the partial date is **after** the year of the first dosing date or the years of the partial date and the first dose date are the same but the month of partial date is **after** the month of the first dosing date, then the first day of the month will be assigned to the missing day.

Missing day, month, and year

- No imputation is needed. The corresponding AE will be included as TEAE.

1.2 Incomplete Stop Date:

If the imputed stop date is before the start date, then the imputed stop date will be equal to the start date.

Missing day and month

- If the year of the incomplete stop date is the **same** as the year of the last dosing date, then the day and month of the last dosing date will be assigned to the missing fields.
- If the year of the incomplete stop date is **prior to** the year of the last dosing date or prior to the year of the first dosing date, then December 31 will be assigned to the missing fields.
- If the year of the incomplete stop date is **prior to** the year of the last dosing date but is the same as the year of the first dosing date, then the first dosing date will be assigned to the missing date.
- If the year of the incomplete stop date is **after** the year of the last dosing date, then January 1 will be assigned to the missing fields.

Missing day only

- If the month and year of the incomplete stop date are the **same** as the month and year of the last dosing date, then the day of the last dosing date will be assigned to the missing day.
- If either the year of the partial date is **not equal to** the year of the last dosing date or the years of the partial date and the last dosing date are the same but the month of partial date is **not equal to** the month of the last dosing date, then the last day of the month will be assigned to the missing day.

2 Imputation of Dates for Prior/Concomitant Medications/Procedures

Partially missing start/stop dates for prior/concomitant medications and partially missing start dates for prior/concomitant procedures will be imputed in the ADaM dataset for prior/concomitant medications/procedures. However, listings of prior/concomitant medications/procedures data will present the date as is, with missing date components left blank.

For prior/concomitant medications, if the stop date is complete with no missing year, month, or day, and the partially missing start date imputed by the rule below is after the stop date, then the start date will be imputed by the stop date.

Partially missing prior/concomitant medication/procedure start dates will be imputed by the earliest possible date given the non-missing field(s) of the date.

Partially missing prior/concomitant medication stop dates will be imputed by the latest possible date given the non-missing field(s) of the date.

3. Imputation of Dates for Pre-specified Medical History

Partially missing start dates for pre-specified medical history will be imputed in the ADaM dataset for pre-specified medical history. However, listings of pre-specified medical history data will present the date as is, with missing date components left blank.

Partially missing pre-specified medical history start dates will be imputed by the earliest possible date given the non-missing field(s) of the date.

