8.2 Procedures for Eliciting, Recording and Reporting Adverse Events

8.2.1 Adverse Event Reporting Period

AEs, including SAEs, will be collected throughout the study period, beginning from the time the subject signs the ICF until the subject's last study visit (normally Follow-up Visit). Any AE or SAE will be followed until the event or its sequelae resolves or becomes stable or otherwise justified by the Investigator in agreement with Relypsa. The Investigator must report any AEs that occur after the protocol specified reporting period if according to the Investigator's assessment there was a reasonable possibility that the AE was related to patiromer or any study procedures.

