8.10 Safety Analyses

8.10.1 Adverse Events

AEs and SAEs will be coded to system organ class (SOC) and preferred term (PT) in accordance with MedDRA 18.1. Adverse event analyses will include only treatment-emergent AEs (TEAEs). A TEAE is defined as any AE that newly appeared or worsened in severity following initiation of study drug administration. If the onset date of an AE is missing, the AE will be considered treatment-emergent unless there is evidence to conclude that it is not. AE listings will include all AEs.

Central laboratory serum pregnancy tests will be done at S1 and Week 12/ET. Local urine pregnancy tests will be done at Randomization/Baseline. Pregnancy is not considered an AE but is reported separately (please see Protocol Amendment 2 Section 8.4 regarding Procedures for Reporting Pregnancy Exposure and Birth Events).

The incidence of TEAEs will be summarized by system organ class (SOC), preferred term (PT) and severity. For those TEAEs that occur more than once during the study period, the maximum severity will be used in the summary by severity.

Descriptive statistical summaries (frequencies and percentages) will be provided by treatment group for the followings:

- Overall summary of TEAEs, including summaries of severity, TEAEs related to study drug, SAEs, SAEs related to study drug, TEAEs leading to study drug modification and TEAEs leading to study drug discontinuation
- Summary of all TEAEs by SOC, PT and severity
- Summary of TEAEs related to study drug by SOC, PT, separately for spironolactone and patiromer/placebo
- Summary of TEAEs leading to study drug modification by SOC, PT, separately for spironolactone and patiromer/placebo
- Summary of TEAEs leading to early study drug discontinuation by SOC, PT, separately for spironolactone and patiromer/placebo

- Summary of SAEs by SOC, PT, and severity
- Summary of SAEs related to study drug by SOC, PT, separately for spironolactone and patiromer/placebo
- Summary of TEAEs of special interest (e.g. allergic reactions, gastrointestinal events, renal events)

A listing for all AEs will be provided, including verbatim term, PT, SOC, severity, whether serious, relationship to each study drug, onset and end date, action taken and outcome of event will be provided. Listings of SAEs and TEAEs leading to study drug modification and to early study drug discontinuation will be provided. Listings will also be provided for events of special interest.

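### For two patterns of incomplete dates, SAP Appendix B omits the stop-date exception that SAP 8.10.1 allows, so literal programming would count AEs that ended in the run-in as treatment-emergent

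*SAP*

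**What the plan says.** AEs are collected before dosing. Protocol 8.2.1 sets the reporting period as "beginning from the time the subject signs the ICF until the subject's last study visit", and the run-in lasts up to 4 weeks, so the database can hold AEs that began and ended before any study drug. Protocol 9.6.5.1 defines a TEAE as beginning or worsening at or after first dose, and SAP 8.10.1 limits the AE analyses to TEAEs.

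SAP 8.10.1 covers a missing onset: "If the onset date of an AE is missing, the AE will be considered treatment-emergent unless there is evidence to conclude that it is not". SAP 7.3 allows the same kind of exception for an onset that equals the first dosing date. SAP 7.4 asks for conservative imputation and refers to Appendix B for the specific rules.

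Three Appendix B rules matter here:

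- **Wholly missing start (1.1):** "No imputation is needed. The corresponding AE will be included as TEAE". No exception is given.
- **End-date cap (1.1):** it begins "If the AE end date is complete with no missing year, month, or day, and a partially missing start date imputed by the rules below" and pulls an imputed start back to the end date when it would otherwise fall later. It needs a complete end date and a partial start.
- **Stop-date override (1.2):** "If the imputed stop date is before the start date, then the imputed stop date will be equal to the start date".

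A start that gives only the year, in the year of first dose, is imputed to the first dosing date. A stop that lacks only the day, in a month other than the last-dose month, is imputed to the last day of that month.

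**The concern.** An event that ended before the first dose cannot be treatment-emergent. Most of the SAP respects this: 8.10.1 and 7.3 allow contrary evidence, and the cap in 1.1 uses a complete stop date as such evidence. Two patterns fall outside that protection.

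With a wholly missing start and a stop before first dose, 8.10.1 gives a non-TEAE and Appendix B 1.1 gives a TEAE. SAP Section 1 ranks the SAP above the protocol, but nothing ranks the body of the SAP above its appendix. The same data could therefore yield two counts, depending on which section the programmer follows.

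With a year-only start and a stop recorded as month and year, the imputed start lands on the first dosing date although the recorded stop month is earlier. Rule 1.2 then shifts the derived stop to match, so the derived dates no longer show the conflict.

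What is at stake is the accuracy of the all-TEAE summaries, including those by severity and of special interest.

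**Working it through.** The plan states no figure on this point, so there is none to reproduce. The check applies the rules as written.

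**Worked example of the second pattern** (dates are illustrative). First dose 20 March 2017; AE start recorded as 2017; AE stop recorded as February 2017.

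1. The start year equals the first-dose year, so the start is imputed to 20 March 2017.
2. The cap requires a complete end date. The end date lacks the day, so the cap does not apply.
3. The stop is imputed to 28 February 2017.
4. The imputed stop is before the start, so rule 1.2 moves it to 20 March 2017.

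The event becomes a one-day event on Day 1, although it is recorded as over in February. The imputed start in step 1 is what makes it a TEAE. Step 4 only removes the inconsistency from the derived dates.

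**Enumeration of date patterns.** Inputs: the Appendix B 1.1 and 1.2 rules; a 28-day run-in (Protocol 3.1.1, up to 4 weeks); and, as assumptions, first dose on each of the 365 days of 2017 and last dose 84 days later. Every pair of start and stop days 1 to 28 days before first dose was taken. A case was kept only if the latest date compatible with the recorded stop precedes first dose.

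- Complete stop: 28 × 29 / 2 = 406 pairs per first-dose date, and 365 × 406 = 148,190.
- Stop lacking the day: the stop must fall in an earlier month. That gives 28 × 29 × 30 / 6 = 4,060 pairs per first-dose month, and 12 × 4,060 = 48,720.
- Year-only stop: the stop must fall in an earlier year, which happens only with January first doses, giving 4,060.

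| Recorded start | Complete stop | Stop lacks day | Stop year only |
|---|---|---|---|
| Wholly missing | 148,190/148,190 (100%) | 48,720/48,720 (100%) | 4,060/4,060 (100%) |
| Year only | 0/148,190 | 44,660/48,720 (91.7%) | 0/4,060 |
| Lacks day | 0/148,190 | 0/48,720 | 0/4,060 |
| Complete | 0/148,190 | 0/48,720 | 0/4,060 |

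Each cell is the share called treatment-emergent although the recorded stop shows that the event ended before first dose. The 100% row restates the rule. The 91.7% is 11/12 (11 × 4,060 = 44,660): with a January first dose the start year is the previous one, so the start is imputed to 31 December and correctly falls before dosing. These are shares of an even enumeration of date patterns, not frequencies expected in the trial.

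If the recorded stop is tested against first dose, as the 8.10.1 exception allows, every cell becomes zero, because only cases with a stop provably before first dose were kept.

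**The case against.** The strongest reply is that the body of the SAP already settles the matter. Section 8.10.1 addresses a missing onset directly, Section 7.3 addresses an onset on the first dosing date (where the second pattern lands), and Section 7.4 delegates only date handling to the appendix. Read together, the appendix gives the default and the body gives the exception. Appendix B also says that listings keep dates as recorded, and nowhere says that the recorded partial date is lost to the programmer. This stands in part. A reader might infer that run-in events will enter the TEAE tables; the documents support that only if Appendix B is programmed literally. But Appendix B itself gives a TEAE instruction without the exception, and it never directs anyone to consult the recorded stop in these two patterns.

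A second reply is rarity. Screening visits are 4 to 10 days apart with AE assessment at each, onset and resolution dates are captured (Protocol 8.2.5), and incomplete data are queried (Protocol 10.1). This stands.

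Three stronger readings are tempting but not supported.

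- **That the related, discontinuation and SAE tables are distorted too.** An event over before first dose cannot have led to stopping study drug. Protocol 8.2.4 makes implausible timing a ground for judging an event not related, so such an event would reach the related table mainly through a missing or mistaken assessment. Onset date is a minimum field on the SAE form (Protocol 8.3.1).
- **That the between-arm comparison is pulled toward no difference.** SAP 8.10.1 plans descriptive frequencies and no test on AEs. Similar additions to both arms would dilute a ratio but barely move a risk difference.
- **That the stop-year rules in 1.2 are a further fault.** One bullet assigns 31 December to a stop year before the last-dose year. The next covers a stop year that precedes the last-dose year "but is the same as the year of the first dosing date, then the first dosing date will be assigned to the missing date". The second can be read as an exception to the first, and no planned table uses AE duration.

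**Conclusion.** The point holds as a gap in wording confined to two date patterns. For a wholly missing start, Appendix B 1.1 and SAP 8.10.1 classify the same event differently whenever the recorded stop precedes first dose. For a year-only start with a month-and-year stop before the first-dose month, Appendix B places the event on the first dosing date against its own recorded stop. For every other pattern checked, the Appendix B rules classify these events correctly.

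The consequence depends on literal programming of Appendix B. In that case the affected events appear in the all-TEAE summaries, including severity and special interest. Their number cannot be derived from the documents and is probably very small. The rule does not differ by arm and efficacy is unaffected. This is a desirable clean-up, not a threat to the trial's conclusions.

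**What to change.** Make three changes in SAP Appendix B:

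1. Replace the last bullet of 1.1 with: *No imputation; the AE is included as a TEAE unless the recorded parts of its stop date show that it ended before the first dose.* This matches 8.10.1.
2. Extend the cap in 1.1 to partial end dates: if the latest date compatible with the recorded stop month and year is before the imputed start, set the imputed start to that date. In the worked example the start becomes 28 February 2017 and the event is not a TEAE.
3. Keep rule 1.2 where the start is fully recorded, and apply it only after the extended cap, so that an imputed start never moves a stop outside its recorded month and year.

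Rule 1.2 should not simply be reversed, because it has a legitimate use. With onset fully recorded as 20 June 2017, last dose on 10 June 2017 and stop recorded only as 2017, the stop is imputed to 10 June and rule 1.2 correctly moves it to 20 June.

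The conservative default stays wherever the recorded stop does not prove that the event ended before dosing. The cost is a few lines of SAP text and the matching derivation code before database lock, with no new data and no protocol amendment. Reported TEAE counts could fall by a few events at most, if date completeness is as good as the visit schedule and data queries suggest.
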